4.2.2 Exclusion criteria

Patients whose CFTR modulator status is unknown or only have one year of CFTR data recorded on the registry will be excluded from the analysis of the effects of CFTR modulators. This is to account for the fact that DIOS data is annualised on the registry, therefore there is no certainty at what time of year DIOS was diagnosed in relation to commencing CFTR modulatory therapy.

Expected duration of participant participation

No individual participant interaction. The CFTR MAGIC study will take place over 24 months, from 1/10/2021 to 30/9/2023.

Participant Withdrawal

Not applicable – no individual participant involvement.

Informed consent

PwCF have given explicit consent to their usual CF teams for their demographic, clinical care, and health outcomes data to be submitted to either the UK or US CF registries.^{15, 16} Written consent is gained from pwCF or their parent/ legal guardian and as part of this they are made aware that the information may be used for research and to plan and improve the quality of clinical care. For the UK CF Trust the use of any data from the registry requires the approval of the Registry Steering Committee.¹⁵ In the US, the request for registry data is reviewed and approved by the Patient Registry/Comparative Effectiveness Research Committee. The project has received approval from both the US and UK registries for patient data to be released to be used for this project. Data is released by the registries as anonymised forms of the data to maintain patient confidentiality. Additional patient specific consent for CFTR MAGIC is therefore not required.

DATA COLLECTION REGIMEN

No new data collection will be necessary within this project. Existing data will be provided by the US and UK CF registries. Requests for the data was approved by the UK CF Trust Registry Steering Committee after reviewing the programme development grant aims, statistical analysis and plan for publication of results. In the US, the request for registry data was reviewed and approved by the Patient Registry/Comparative Effectiveness Research Committee and was subject to peer review. Data will be provided as anonymised data so the individuals cannot be identified and analysed using Stata software.

ACCESS TO REGISTRY DATA

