Trends in the registries will be described, however no statistical tests will be used to directly similarities and differences between the registries over time due to the distinctions between the two registries.

2. The patient demographics lists above will be used for demographic propensity matched controls
 - Patient-level data will be used to create registry-based control groups with similar demographic features to those taking CFTR modulators. Due to the restricted genotype eligibility criteria for the earliest CFTR modulator, Ivacaftor, the CFTR user group may have distinct features compared to the overall registry. In addition the restrictive indications for the use of Ivacaftor and limited number of DIOS events on the registry will therefore mean the number of events within exposed individuals may be low. Therefore propensity scores will be used to define a control group of non-eligible non-users that are otherwise representative at the year CFTR modulator exposure was commenced. See directed acyclic graph (DAG) below.
 - Nearest neighbour matching, caliper 0.2 standard deviation, 3:1 ratio of unexposed to exposed will be used for propensity matching. Matching will be performed according to first year of exposure using all pre-exposure information in wide format. Standardised mean difference will be used to check covariate balance between matched and unmatched populations. Average treatment effect of treated will be used to assess matching specification with alternates.

Directed acyclic graph (DAG) for the potential relationship of CFTR modulator and DIOS

Objective 2: Determine the effect of CFTR modulators on DIOS and PERT, using an population-level controlled interrupted time series

This protocol is confidential and the property of the University of Nottingham. No part of it may be transmitted, reproduced, published, or used by others persons without prior written authorisation from the University of Nottingham

Objective 2 will investigate the effect of CFTR modulator intervention on the rate on PERT use and DIOS incidence.

We will test the hypotheses that;

- a) Ivacaftor introduction (2012) in patients with gating mutations lowered the rate of PERT use and the incidence of DIOS in both registries, and that
- b) The introduction of Orkambi (Ivacaftor/Lumacaftor) for those homozygous for F508del mutations in the US (2015) lowered the rate of PERT use and the incidence of DIOS. Specifically, we hypothesise a downward trend, no lag.

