Hypothesis 2b will be explored in the US population only given that introduction of Orkambi was delayed in the UK until 2019.

ITS will explore proportion of DIOS events at population level in the CFTR modulator population and the propensity score defined comparator population. ITS will explore proportion of overall PERT usage (user/non user), and the proportion of individuals with a reduction in weight standardised PERT dose (decrease/no decrease)

- Sensitivity will include distributed lag of 1-3 (years) to account for the possibility that exposure time in the first year was not sufficient for a change in outcome, compared to non-lagged, and to explore PERT usage status change to non-user.
- Autoregression will be visually assessed and effects will also be compared with those from autoregressive model (Prais-Winsten).

Analysis will be performed overall and stratified by 1) Age group (<6, 6-11, 12+) to account for clinical distinctions in pre-schoolers, school age children and adults, 2) History of meconium ileus, as these individuals are at higher risk of DIOS events.

Analysis of hypothesis 2a: Controlled interrupted time series: ivacaftor analysis in G551D criteria

- Segmented regression (with and without lag term), and Prais-Winsten regression for serial correlation.
- Impact model: downward trend (no/minimal level change)
- Model includes: pre intervention, level change, post intervention: interaction with covariates (age, gender, disease status).
 - Pre intervention: no CFTR modulator (time control)
 - Post intervention: ivacaftor (minimum 6 months)
 - US 2007-2011:2012-2017
 - UK 2007-2011:2012-2017
- Propensity score matched controls (demographic control)

Analysis hypothesis 2b. Interrupted time series: lumacaftor/ivacaftor analysis in US F508del subgroup.

- Hypothesis, downward trend no lag.
- Pre intervention no CFTR modulator: (time control)
- Post intervention: lumacaftor/ivacaftor, minimum 6 months
 - US 2007-2014:2015-2017
- Propensity score matched controls (demographic control)

- Parallel plot of UK F508del homozygous subgroup (indirect genotype control)

Objective 3: Determine the effect of CFTR modulators on DIOS and PERT: patient-level time series

This will focus on patient level associations to complement the registry level findings. We will specify explore associations in the incidence of PERT usage and DIOS events between 2012 and 2017 in individuals with CFTR modulators, compared to propensity matched controls.

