- UK 2012-2017 & US 2012-2017 separately
 - Exposure: ivacaftor (minimum 6 months) vs No modulator (matched)
 - Secondary comparator: ivacaftor alone and lumacaftor/ivacaftor (US only)
- DIOS events:
 - Outcome: Patient-level annualised DIOS event counts
 - Multilevel Poisson Regression model for count data (or negative binomial) by year
 - Incidence rate ratio (frequency of DIOS events)
 - Adjusted analysis for main covariates (DAG – Fig 2), also include history of DIOS as pre-exposure time will not be modelled.
 - Contingency table with χ^2 /fisher if insufficient events for modelling.
- PERT usage:
 - Outcome: Patient-level annualised PERT dosage standardised by weight
 - Secondary: decreased PERT usage vs continued/increased
 - Multilevel linear regression for continuous data
 - Secondary: multilevel logistic regression for dichotomised data
 - Adjusted for main covariates (DAG – Fig 2), also include history of DIOS as pre-exposure time will not be modelled.
- Sensitivity analyses
 - CFTR modulator start year excluded, finite distributed lag (1-3 years).
 - Long run propensity (cumulative 0-3 years), cumulative modulator exposure.

Sample size and justification

N/A.- registry study

ADVERSE EVENTS

This is a registry study therefore there is no individual participant interaction and as such no associated risk or burden for participants in the study. Patient's data will be provided as anonymised data and therefore patient confidentiality will be maintained.

ETHICAL AND REGULATORY ASPECTS

ETHICS COMMITTEE AND REGULATORY APPROVALS

Requests for the data required the approval of the UK CF Trust Registry Steering Committee after reviewing of the programme development grant aims, analysis and plan for publication of results. In the US, the request for registry data was reviewed and approved by the Patient Registry/Comparative Effectiveness Research Committee and was subject to peer review.

The data will be provided from the registries as anonymised data so the individuals cannot be identified. Specifically, the CF Foundation requires that no individually identifiable information from the CF Foundation Patient Registry shall be included in publications and other written products and data must be presented in the aggregate. Both US and UK registries require that all tables or presentation of the data generated from registry data should include a patient count of five or more in each cell and any values less than 5 should be represented as <5.

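### The 6-month minimum exposure rule selects the modulator group on information arising after the matching point, has no stated counterpart in controls, and no listed analysis is stated to keep early stoppers

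*Combined protocol and SAP*

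**What the plan says.** The Objective 3 analysis plan sets out the contrast as "Exposure: ivacaftor (minimum 6 months) vs No modulator (matched". Objective 2a has "Post intervention: ivacaftor (minimum 6 months" and Objective 2b has "Post intervention: lumacaftor/ivacaftor, minimum 6 months", so the minimum runs through all the modulator-effect analyses.

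Controls are described under Objective 1, item 2. Propensity scores are to "define a control group of non-eligible non-users that are otherwise representative at the year CFTR modulator exposure was commenced". On timing, "Matching will be performed according to first year of exposure using all pre-exposure information in wide format"; the ratio is 3:1 unexposed to exposed.

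Section 4.2.2 adds that patients with unknown modulator status or who "only have one year of CFTR data recorded on the registry will be excluded from the analysis of the effects of CFTR modulators". The reason given is that DIOS is recorded annually, so "there is no certainty at what time of year DIOS was diagnosed in relation to commencing CFTR modulatory therapy".

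The Objective 3 sensitivity analyses exclude the modulator start year, apply lags of 1-3 years, and look at cumulative exposure. Start dates and treatment interruptions are among the variables requested under Study Design.

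Several things are not stated: when exposed follow-up begins; whether the first 6 months count as exposed time; whether 6 months means a continuous spell, a running total or a rule for each calendar year; and what happens to initiators who do not reach it.

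**The concern.** Whether a patient completes 6 months on drug is known only after the point at which controls are matched. Matching on pre-exposure data, and adjusting for history of DIOS, cannot balance a selection made later.

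A patient who starts and stops within 6 months appears to fit neither group: too little exposure for the modulator group, yet not a non-eligible non-user. On the natural reading such patients drop out of the exposed side, while their counterparts among the controls, who cannot be identified, stay in. If stopping is related to gut problems, the remaining modulator users would show less DIOS and different PERT use even if the drug did nothing.

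This matters because the protocol hypothesises a downward effect and expects few events in exposed individuals. A shift produced by a handful of excluded events could be read as confirmation.

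**Working it through.** The plan gives no sample size, expected effect or discontinuation rate, so there is no figure to reproduce. The checks below ask what rate ratio (IRR) would appear. All values of d, r, q, T, f, m and k are assumptions.

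**1. Selection on persistence, no true effect.** Let d be the share of initiators failing the 6-month rule, and r their DIOS rate relative to persisters, after matching and adjustment. Controls reflect the full mix, with relative rate (1 − d) + d·r; the exposed group contains persisters only, with relative rate 1. Hence

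apparent IRR = 1 / [(1 − d) + d·r].

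For example, d = 10% and r = 2 give 1/(0.90 + 0.20) = 0.91.

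| d | r = 0.5 | r = 1 | r = 2 | r = 3 |
|---|---|---|---|---|
| 5% | 1.03 | 1.00 | 0.95 | 0.91 |
| 10% | 1.05 | 1.00 | 0.91 | 0.83 |
| 20% | 1.11 | 1.00 | 0.83 | 0.71 |

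The sign depends entirely on r. The formula also assumes that the difference in rate lasts throughout follow-up.

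The same reasoning applies to weight-standardised PERT dose. If early stoppers' mean dose exceeds that of persisters by Δ, the control mean is higher by d·Δ and the apparent modulator effect is −d·Δ, that is 5-20% of Δ for d of 5-20%.

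**2. Guaranteed time, no true effect.** If a share q of patients with DIOS in the first 6 months thereby fail the rule, and follow-up is T years, apparent IRR = (T − 0.5q)/T. With T = 3 this is 1.00 (q = 0), 0.98 (q = 0.1), 0.92 (q = 0.5) and 0.83 (q = 1).

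**3. Early death or loss among controls, no true effect.** Let m be the yearly loss and k the relative DIOS rate in those lost, with 0.25 years contributed by those lost in the first 6 months and 3 years by the rest. Then h = 1 − √(1 − m), and the relative control rate is [0.25hk + 3(1 − h)] / [0.25h + 3(1 − h)]. At m = 5% and k = 5, h = 0.0253 and the rate is 2.9557/2.9304 = 1.0086, so the apparent IRR is 0.99. Smaller values give results closer to 1. Removal of early stoppers is therefore the larger issue; the missing survival condition for controls matters little by itself.

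**4. Dilution, which works the other way.** If the true IRR is 0.70 and the start year counts as exposed with only a fraction f of it on drug, apparent IRR = [(T − 1)·0.7 + f·0.7 + (1 − f)]/T. With f = 0.5 this is 0.85 (T = 1), 0.75 (T = 3) and 0.73 (T = 5).

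**The case against.** The strongest reply is that the direction of bias cannot be read from the documents. A reader might infer that the rule necessarily favours the modulator. That requires early stoppers to have more DIOS than persisters, which the protocol nowhere says; at r = 1 there is no bias, and below 1 it reverses. This reply stands.

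A reader might also call this classic immortal-time bias. The outcome is an annual count, and DIOS is not said to end exposure or follow-up, so guaranteed time arises mainly if DIOS, death or loss stops a patient reaching 6 months. Nor should 6 months be set against the mean exposures of 2 and 1.3 years in the Background: those belong to an earlier cited registry study, whereas Objective 3 covers 2012-2017. This cohort's mean exposure is not given.

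The one-year-of-data exclusion is not worded as applying to exposed patients only, so it may be a partial minimum-data rule for both groups. It does not bring early stoppers back. Matching on pre-exposure information and adjusting for history of DIOS also shrink r, so a crude relative rate of 2 or 3 would overstate the problem.

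Excluding the start year may remove much of any guaranteed time. It is only a sensitivity analysis, though, and it does not restore early stoppers. Finally, the minimum may be intended only to classify registry years as exposed. That reading is possible, but the text does not settle it, and the choice should not be left until the data have been seen.

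**Conclusion.** The concern holds as a possible bias of uncertain direction. The exposed group is defined by a post-anchor condition with no stated counterpart in controls, and no listed analysis is stated to retain all initiators. Under no effect and with 5-20% of initiators removed, the apparent IRR runs from about 0.71-0.95 (early stoppers at 2-3 times the rate of persisters) through 1.00 (equal rates) to 1.03-1.11 (half the rate). These figures rest on assumed d and r, with r taken as the difference remaining after matching and adjustment and lasting throughout follow-up. A shift towards the modulator is plausible if gut problems prompt stopping; the documents do not establish that it occurs. The change is worth making because it is cheap and the needed data are already requested.

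**What to change.** In the analysis plan:

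- Set time zero as the index (first exposure) year for each exposed patient and assign the same index year to the matched controls.
- Make the main comparison all initiators, whatever their duration of treatment, against those controls. Handle the start year identically in both groups, whether kept or excluded.
- Keep the 6-month rule as an on-treatment sensitivity analysis. State whether it means continuous, cumulative or per-year exposure, and require controls to be alive and under registry follow-up at the matched point. Set that point by calendar year, since DIOS is recorded annually and matching is by year.
- Report how many initiators fail the rule and their DIOS and PERT outcomes, within the registries' small-cell limit, so that d and r can be judged from data where counts allow.

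The cost is protocol wording, slight dilution of any true effect by early stoppers and, if the start year is excluded from the main analysis, loss of some events where the protocol already expects few.

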Cystic fibrosis (CF) is an autosomal recessive disorder, caused by mutations to the cystic fibrosis transmembrane conductance regulator (CFTR) gene encoding for the CFTR protein. CF affects around 10,000 people in the UK with a life expectancy of 49 years in 2019.¹ Although CF is a multi-system disorder, its impact on the respiratory track and gastrointestinal (GI) system are of particular clinical importance.² In the gut, CFTR mutations result in pancreatic exocrine insufficiency in around 85% infants resulting in maldigestion and impaired nutrition,³ with adequate nutrition in CF linked to life expectancy.⁴ Due to the success of the newborn screening programme in the UK most people with CF (pwCF) are now identified within the first few weeks of life and commenced on pancreatic enzyme replacement therapy (PERT). Cystic fibrosis has a high associated treatment burden, with PERT in particular contributing to this, with patients often have to take 25-30 capsules per day.⁵ However, despite this almost all pwCF experience GI symptoms including abdominal pain, flatulence, constipation and bloating,⁶ with two thirds missing work or school because of this.⁷ This is why ‘How can we relieve gastro-intestinal symptoms, such as stomach pain, bloating and nausea in people with Cystic Fibrosis?’ was identified as one of the top 10 research priorities in a James Lind Alliance Priority Setting Partnership (JLA PSP) in CF conducted by our group.⁸

In addition, other GI manifestations affecting pwCF include distal intestinal obstructive syndrome (DIOS), CF related liver disease (CFRD) and pancreatitis. DIOS is a severe GI complication in CF defined as a complete intestinal obstruction with an ileo-caecal mass and abdominal distension, thought to result from the accumulation of faecal material at the ileo-caecal valve.⁹ It affected 5.7% pwCF in the UK (2.5% in <16 years and 7.7% in adults)¹ and 2.1% in the US (<18 years 1.7%, adult 2.4%)¹⁰ in 2019. However, the pathology underlying DIOS and GI symptoms are currently not well understood.

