Data will be in the form of registry data provided from the US and UK CF registries from the period 2007-2017. These datasets will be provided as encrypted data via the registries preferred data sharing platform (Box.com or similar). Both registries have already reviewed and approved the sharing of their data for use within this project.

Criteria for terminating the registry data

No data will be archived in a data repository following project completion due to the requirements of the CF Foundation and CF Trust registries. The CF foundation considers the project to be completed after 3 years. After this time data files and any copies of the files will be destroyed. The CF Foundation will be provided with written confirmation of destruction of the data and completion of the project or alternatively provided with a sufficient justification for continuation of the project if required. The CF Foundation maintains copies of all data sets sent to researchers and can provide the data again if required for auditing purposes. The CF Trust requires all data to be destroyed at the end of the project and that all data forms must be permanently destroyed within 12 months of the date of supply unless approval has been granted by the UK CF Registry Research Committee for an extension.

STATISTICAL ANALYSIS

Data will be provided from the UK and US registries as an encrypted file and analysis will be performed using Stata software. Statistical analysis will be completed by members of the research team, led by [name]. A full plan for statistical analysis is described below.

[figure not shown]
Objective 1: Assess the rate of PERT use and the incidence of DIOS in UK and US registries 2007-2017

1. Descriptive analysis 2007-2017 to include:
 - Yearly cumulative incidence of DIOS and prevalence of PERT usage in the UK and US (2007-2017)
 - PERT use will be dichotomised (i.e use/no use)
 - Incidence of DIOS (event/no event)
 - **Plotted by year**, separated by registry
 - Stratification by age range (<6, 6-11, 12+)

- Patient demographics of DIOS and PERT reporting
 - The distribution of yearly reported incidence events and use prevalence (%) will be addressed according to age groups, sex, BMI, ethnicity, antibiotic use, comorbidities (including Pseudomonas colonisation, GI complication history, GI co-morbidities such as CFRD and CFRLD), FEV₁ lung function, centre (where available, pseudo ID).

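### Objective 3's main PERT dose model states no score for years off PERT and does not fix PERT status before exposure, so its estimate turns on an unstated choice

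*Combined protocol and SAP*

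**What the plan says.** All references are to the combined protocol and SAP.

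- **Outcome and model.** Under Statistical Analysis, Objective 3, PERT usage, the outcome listed first is "Outcome: Patient-level annualised PERT dosage standardised by weight", with "Multilevel linear regression for continuous data". A binary outcome follows: "Secondary: decreased PERT usage vs continued/increased", by multilevel logistic regression.
- **Covariates.** The PERT model adjusts for the main covariates in the DAG (figure not shown), and the text adds: "also include history of DIOS as pre-exposure time will not be modelled". No earlier PERT status or dose is named.
- **Population.** The eligibility criteria admit CF patients of every genotype. The exclusions concern modulator status and length of record, not PERT. The Background states that "CFTR mutations result in pancreatic exocrine insufficiency in around 85% infants", so some patients may never have needed PERT.
- **Matching.** Controls are matched 3:1 by propensity score in the first exposure year. The listed characteristics do not name PERT, although the text also refers broadly to all information from before exposure.
- **Stopping is foreseen.** Objective 2 hypothesises that modulators lower the rate of PERT use. It analyses user/non-user proportions at population level, and its lag sensitivity analysis is partly "to explore PERT usage status change to non-user".

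No section says whether a year off PERT counts as zero, missing or excluded in the Objective 3 dose model.

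**The concern.** A linear model for dose needs a number for every patient-year. Two groups have no obvious one: patients who stop PERT during follow-up, and patients who were never on it. There are two natural ways to run the model as written.

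- **Off-PERT years left blank.** The regression drops those records. The comparison is then conditional on still taking PERT, which is determined after exposure and is part of the outcome. Stopping is the largest possible fall in dose, and it leaves the estimate. A patient who stops midway keeps only the earlier on-PERT years.
- **All non-users scored zero.** Stoppers are kept, but never-users enter as fixed zeros that cannot fall. They widen the spread. With no baseline PERT term named, any difference between arms in the share of never-users passes into the treatment contrast. Controls are patients ineligible by genotype, and the plan itself warns that the modulator group may differ from the rest of the registry, so balance cannot be assumed.

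Two competent analysts could follow the text and report materially different main results.

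**Working it through.** **Inputs.** The documents give no sample size, power, effect size, dose SD or stopping rate for this analysis, so there is no figure of the plan's to reproduce. From the documents: 3:1 matching, and about 85% pancreatic insufficiency in infants, taken here as up to about 15% never on PERT. Everything else below is assumed.

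**1. Dropping off-PERT years.** Set mean dose per kg among baseline users to 100. Let s be the share of exposed users who stop and r the proportional fall among those who continue. Assume that controls do not stop and that stopping is unrelated to prior dose.

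- Stopped years scored 0: effect = -100 × [s + (1 - s)r]
- Stopped years dropped: effect = -100 × r

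| s | r | Scored 0 | Dropped | Share kept |
|---|---|---|---|---|
| 2% | 10% | -11.8 | -10.0 | 85% |
| 5% | 5% | -9.75 | -5.0 | 51% |
| 10% | 5% | -14.5 | -5.0 | 34% |
| 20% | 5% | -24.0 | -5.0 | 21% |
| 10% | 0 | -10.0 | 0 | 0% |

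Over s from 2% to 20% and r from 0 to 10%, between 0% and 85% of the effect is kept.

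**2. Scoring every non-user zero.** With 15% never on PERT in both arms, the effect is 0.85 times the zero-scored effect in users; for s = 10% and r = 0, 0.85 × -10 = -8.5. That is the correct average over all treated patients, so the smaller number is not a bias. The cost is precision.

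A simulation compared the patient's mean dose over 4 years, exposed minus control: 500 exposed, 1,500 controls, between-patient SD 40, within-patient SD 15, 15% never-users in each arm, 300 replicates. Estimates are shown with standard errors, and z is in absolute value.

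| s, r | All non-users 0 | z | Baseline users, stoppers 0 | z | Loss in z |
|---|---|---|---|---|---|
| 10%, 0 | -8.59 (2.80) | 3.07 | -10.07 (2.61) | 3.86 | 20.5% |
| 5%, 0 | -4.21 (2.73) | 1.54 | -4.95 (2.45) | 2.02 | 23.7% |
| 5%, 5% | -8.17 (2.63) | 3.11 | -9.83 (2.35) | 4.18 | 25.7% |
| 10%, 10% | -15.99 (2.59) | 6.17 | -18.83 (2.40) | 7.85 | 21.3% |

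With off-PERT doses missing, the same four scenarios gave 0.01, 0.04, -5.07 and -9.78, which is -100r in each case apart from simulation error.

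The first row can be checked by hand. The variance of a user's 4-year mean is 40² + 15²/4 = 1,656.

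- Baseline users (425 and 1,275): exposed variance 0.9 × 1,656 + 0.9 × 0.1 × 100² = 2,391. SE = √(2,391/425 + 1,656/1,275) = 2.63, so z = 10/2.63 = 3.80.
- All patients: exposed variance 0.765 × 1,656 + 0.765 × 0.235 × 100² = 3,065; control variance 0.85 × 1,656 + 0.85 × 0.15 × 100² = 2,683. SE = √(3,065/500 + 2,683/1,500) = 2.81, so z = 8.5/2.81 = 3.02.
- Loss: 1 - 3.02/3.80 = about 20.5%, as simulated.

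**3. Imbalance under zeros for all.** If the never-user share differs by d between arms, zeros alone create a difference of 100 × d. For d = 5 percentage points that is 5 units, as large as a true 5% fall in every user. Its sign depends on which arm holds more never-users.

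**The case against.** The strongest reply is that this is a gap in wording. The plan requests both PERT dosage and usage and codes use/no use for Objective 1, so an off-PERT year can be identified and zero is a natural dose for it. If zeros are entered, stoppers are kept and the loss in step 1 does not arise. A separate data management plan is mentioned and the DAG is not shown; either could hold a derivation rule or a PERT covariate. Matching on all pre-exposure information might also balance PERT status. All of this stands as possibility. But the section presents itself as the full statistical plan, and a rule that decides the main estimate belongs there.

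Three stronger readings are tempting, and the documents do not support them.

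- *An effect through stopping would be invisible in the study.* The Objective 3 binary outcome would most naturally class stopping as a decrease, although it does not say so, and the Objective 2 user/non-user series addresses it directly at population level. Neither repairs the dose estimate.
- *Responders are lost from the exposed arm only.* No stopping rate is given for either arm. That controls rarely stop is an assumption of the working.
- *Zeros for everyone is wrong.* It is a legitimate whole-population target, consistent with the broad eligibility. The objection to it is lost precision and exposure to baseline imbalance.

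The simulation also compares unadjusted patient means, whereas the plan has an adjusted multilevel model after matching. Matching or adjusting on PERT status, if done, could reduce the loss in step 2.

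**Conclusion.** The concern holds for Objective 3's main dose estimate and should be settled before analysis. As written, the model covers all matched patients, names no earlier PERT status or dose, and leaves off-PERT years unscored although the plan anticipates stopping. If those years are dropped, the estimate is r in place of s + (1 - s)r, given that stopping is unrelated to prior dose and controls rarely stop. If all non-users score zero, the estimate is valid for the whole population. Its z value is then about 20-26% smaller under the assumed inputs than in baseline users, and it moves by 1 unit on the index of 100 for each percentage point of imbalance in never-users.

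The actual size cannot be found from the documents: the stopping rates, dose spread, number exposed and never-user share in the ivacaftor group are not given, and the 85% figure is for infants generally. A reader might infer that the study as a whole would miss a stopping effect; the other PERT analyses rule that out.

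**What to change.** In Objective 3, PERT usage, state that:

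1. the dose analysis set is patients recorded as on PERT in the last pre-exposure (match) year, in both arms. Apply this before matching, or match exactly on PERT status; restricting afterwards would break the 3:1 matched sets;
2. a later year with recorded non-use scores dose 0 and stays in the model. Dose is missing only when PERT use itself is unrecorded. Use robust standard errors;
3. the model adjusts for pre-exposure dose per kg;
4. the effect among continuing users is a sensitivity analysis, labelled as conditional on continuing.

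The cost is SAP wording, one derived variable from PERT fields already requested, and a matching step within PERT users or exact on PERT status. The result then applies only to patients on PERT at baseline, and never-users leave the dose model. The zeros make the outcome less normal; robust standard errors protect the inference but do not improve the fit of a linear model.
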